**Listing 23.2: RECIST assessments - lesions**

patient.patient_no	registration.registration_arm_randomized	tm_st_tm_st_st_nr	tm_st_tm_st_date	tm_le_tm_le_loc	tm_le_tm_le_loc_ext	tm_le_tm_le_method	tm_le_tm_le_size	tm_le_tm_le_tumor_type	tm_st_tm_st_measures_assessment	tm_st_tm_st_immeas_assessment
Patient No.	Arm	Staging No.	Date	Localization	Detailed information about localization	Method	Size of lesion if measurable [mm]	Tumor type if non-measurable	Assessment measurable lesions	Assessment non-measurable lesions

**Listing 24: PFS, OS, and TFTS**

patient.patient_no	registration.registration_arm_randomized	registration.registration_registered_at	endofstudy.endofstudy_last_contact_date		ae.ae_irino_inter_date, ae.ae_fa_inter_date, ae.ae_ffu_inter_date, ae.ae_ce_inter_date		tm_st.t_m_st_d ate		endofstudy.endofstudy_death_date			
Patient No.	Arm	Date of randomization	Date of last contact	Treatment discontinuation for any reason [yes/no]	Date of (first) discontinuation	Progress [yes/no]	Date of progression	Death [yes/no]	Date of death	PFS [months]	OS [months]	TFTS [months]

End of treatment:**Listing 25.1: EOT - resection and new therapy**

patient.patient_no	registration.registration_arm_randomized	eut.eot_date	eut.eot_end_reason(_other_spec)	eut.eot_resection_date	eut.eot_resection_status	eut.eot_tumor_th	tumor.tumor_therapy	tumor.tumor_start	tumor.tumor_end(nd)
Patient No.	Arm	EOT evaluation date	Reason for EOT	Resection date if resection performed	Resection status if resection performed	New tumor therapy since last study treatment [yes/no]	New therapy	Start date of new therapy	End date of new therapy

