2.6 Study Rationale

As mentioned before, it has been shown, that *RAS* mutated status of mCRC present at diagnosis mostly converts to wild-type status during the first line chemotherapy in liquid biopsy. Since treatment options for patients with mCRC are limited, especially for patients with *RAS* mutations, which are not be considered eligible for therapy with EGFR antibodies, this study will use regular monitoring of *RAS* status by liquid biopsy to treat patients according to their actual *RAS* status. Thus, mCRC patients with mutant *RAS* will receive standard first line chemotherapy (FOLFIRI) according to guidelines recommending a double or triple chemotherapy in case of *RAS* mutated mCRC until the conversion of *RAS* to wild-type is observed [43]. Wild-type patients will then be randomized to continue the existing treatment regimen (Control Arm) or to switch to the EGFR antibody cetuximab in combination with FOLFIRI (Experimental Arm) until re-conversion to mutant *RAS*. In both arms the treatment strategy will be followed until PD, unacceptable toxicity, withdrawal of informed consent or death, whichever occurs first.

This study design of therapy adaptations as performed in the experimental arm has 2 advantages:

1. Patients with initially mutant *RAS* can benefit from anti-EGFR treatment due to conversion of *RAS* status during standard first line therapy and to the data that the treatment with an EGFR antibody is the most effective treatment option for patients with left-sided *RAS* wild-type mCRC.
2. Emerging resistance to treatment with cetuximab which may limit the clinical benefit is bypassed by early switching to chemotherapy (FOLFIRI) without cetuximab before PD. This ensures that patients with *RAS* mutations in liquid biopsy do not receive EGFR antibodies according to approval.
3. Steps 1 and 2 may be repeated as long as the patient does not experience disease progression.

Therefore, it is expected that patients in the experimental switch arm will have a longer PFS compared to control arm.

The randomized study design allows direct comparison of standard therapy and switch treatment without bias by investigator or patient characteristics.

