One or two cycles of FOLFIRI/mFOLFIRI may be administered in the pre-screening period before the result of the RAS analysis is available. Patients with any RAS mutation who fulfill all the eligibility criteria will be enrolled into the pre-randomization phase. Patients with RAS wild-type status will be considered screening-failures.

Randomized phase

Control arm:

FOLFIRI (q14d):

- Irinotecan 180 mg/m² iv, 30 - 90 min on day 1
- Folinic acid (racemic) 400 mg/m² iv, 120 min on day 1

- 5-FU 400 mg/m² bolus on day 1
- 5-FU 2400 mg/m² iv over 46 h on day 1-2

OR

mFOLFIRI (q14d):

- Irinotecan 180 mg/m² iv, 30 - 90 min on day 1
- Folinic acid (racemic) 400 mg/m² iv, 120 min on day 1
- 5-FU 2400 mg/m² iv over 46 h on day 1-2

Experimental arm (switch arm):

FOLFIRI (q14d) + cetuximab (q1w):

- Irinotecan 180 mg/m² iv, 30 - 90 min on day 1
- Folinic acid (racemic) 400 mg/m² iv, 120 min on day 1
- 5-FU 400 mg/m² bolus on day 1
- 5-FU 2400 mg/m² iv over 46 h on day 1-2
- Cetuximab initially 400 mg/m² as a 120 min infusion (\leq 5 mg/min) on day 1; subsequently 250 mg/m² iv as a 60 min infusion every week (\leq 10 mg/min)

OR

mFOLFIRI (q14d) + cetuximab (q1w):

- Irinotecan 180 mg/m² iv, 30 - 90 min on day 1
- Folinic acid (racemic) 400 mg/m² iv, 120 min on day 1
- 5-FU 2400 mg/m² iv over 46 h on day 1-2
- Cetuximab initially 400 mg/m² as a 120 min infusion (\leq 5 mg/min) on day 1; subsequently 250 mg/m² iv as a 60 min infusion every week (\leq 10 mg/min)

If *RAS* wild-type converts to *RAS* mutant:

FOLFIRI or mFOLFIRI (q14d) as stated above

If *RAS* mutant converts to *RAS* wild-type again:

FOLFIRI or mFOLFIRI (q14d) + cetuximab q1w as stated above

In case one of the substances has to be stopped due to toxicity, the others should be continued, if tolerable for the patient.

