5.4.1 Permanent Treatment Discontinuation

Patients will receive study treatment until any of the following occur:

- 3 years of study treatment
- Patient experiences PD according to RECIST v 1.1 criteria. Individual decision concerning discontinuation should be performed at the discretion of the treating physician
- Patient experiences unacceptable toxicity or an adverse experience that would, in the investigator's or sponsor's judgment, make continued administration of the study regimen an unacceptable risk

- Situations requiring a therapeutic intervention that is not permitted by the treatment plan
- Development of an intercurrent illness or situation which would, in the judgement of the investigator, affect assessments of clinical status and study endpoints to a significant degree
- For WOCBP: Pregnancy
 - All WOCBP should be instructed to contact the investigator immediately if they suspect they might be pregnant (e.g., missed or late menstrual period) at any time during study participation.
 - The investigator must immediately notify the delegated CRO (who will inform the sponsor / coordinating investigator) in the event of a confirmed pregnancy in a patient or in a partner of a patient participating in the study.
- Request by the patient to stop the treatment
- Patient is considered by the investigator or the sponsor to be significantly noncompliant with the requirements of the protocol (e.g., patient becomes pregnant)
- Study is closed or terminated
- Patient is lost to follow-up
- Investigator's decision
- At the specific request of the sponsor

In case of prolongation of any treatment delay beyond 28 days after the last administration of the chemotherapy as a result of delayed hematological recovery or/and non-hematological adverse events (AEs), permanent treatment discontinuation should be decided after consultation with the coordinating investigator.

Note: A temporary interruption in study medication due to an AE is not considered to be permanent discontinuation of investigational product.

The reason for discontinuing study treatment must be clearly documented in the patient's medical record and recorded on the case report forms (CRF). Patients for whom the study treatment has been permanently discontinued will continue in the study unless they meet the criteria for study withdrawal (below).

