- If the reaction has resolved to ≤ grade 2, resume at a lower dose level (200 mg/m² after the 2nd occurrence and 150 mg/m² after the 3rd occurrence).
- If the reaction does not resolve to ≤ grade 2, permanently discontinue cetuximab treatment.

c) 4th occurrence of severe skin reaction:

- Permanently discontinue cetuximab treatment.

If cetuximab has to be discontinued permanently patients will receive FOLFIRI chemotherapy until PD or conversion to RAS-mutant without PD. In this case patients will receive FOLFIRI.

When new conversion to *RAS*-wild-type is observed, patients will start again with FOLFIRI + cetuximab, as long as there are no reasons for permanent discontinuation of cetuximab.

7 Clinical Examinations

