TFTS: Defined as the time from date of randomization to failure of treatment strategy, i.e., treatment discontinuation for any reason, including disease progression, withdrawal of consent, treatment toxicity, patient preference, loss to follow up, or death from any cause.

An AE will be called treatment-related if its occurrence is definitely, probably, or possibly related to the administration of any study treatment.

Note that a year is equal to 365 days, a month is equal to 30.4 days, and a week is equal to 7 days for duration calculations.

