## 5 Mock-ups for tables, listings, and figures

The following TLF are planned. The fields marked in checked grey (listings) and the grey text in curly braces (tables) show the programmer where the parameter to be analyzed may be found and will not appear in the report.

Regarding listings, alternative choices such as yes or no, male or female, and positive or negative will not be displayed, but units will be given as shown below. Furthermore, abbreviations listed in chapter 1 will be used for legibility.

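### SAP Listing 24 takes the discontinuation date that feeds TFTS only from per-drug adverse-event dates, while TFTS counts treatment discontinuation for any reason (minor)

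*SAP*

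**What the plan says.** SAP 4.12 defines TFTS as the time from randomization to "treatment discontinuation for any reason, including disease progression, withdrawal of consent, treatment toxicity, patient preference, loss to follow up, or death from any cause". Protocol 10.1.2 gives the same definition.

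Listing 24 (SAP 5.2) prints TFTS beside PFS and OS. Its column for the date of (first) discontinuation carries one source entry: "ae.ae_irino_inter_date, ae.ae_fa_inter_date, ae.ae_ffu_inter_date, ae.ae_ce_inter_date". These are adverse-event-form dates, one each for irinotecan, folinic acid, 5-FU and cetuximab. SAP 5 explains that such entries "show the programmer where the parameter to be analyzed may be found and will not appear in the report".

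On stopping single drugs, Protocol 5.1 says: "In case one of the substances has to be stopped due to toxicity, the others should be continued, if tolerable for the patient". Protocol 6.2 adds: "If cetuximab has to be discontinued permanently patients will receive FOLFIRI chemotherapy until PD or conversion to RAS-mutant without PD". Protocol 2.6 describes how long the strategy as a whole runs: "In both arms the treatment strategy will be followed until PD, unacceptable toxicity, withdrawal of informed consent or death, whichever occurs first". Among the reasons for permanent discontinuation, Protocol 5.4.1 includes "Request by the patient to stop the treatment" as well as investigator and sponsor decisions. It also notes that a temporary interruption for an adverse event is not a permanent discontinuation.

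**The concern.** The definition covers every reason for ending treatment; the stated data source covers one. The source is also split by drug and read through the word first, whereas the endpoint concerns the strategy. A program written from the mock-up could therefore go wrong in two opposite ways. It could leave a non-adverse-event stop undated, or it could date the failure of the strategy at the first problem with a single drug.

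TFTS is one of three time-to-event endpoints that the SAP still reports, in Listing 24 and Figure 4. With at most seven values, one wrong or missing date would be visible in the plot.

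**Working it through.** No sample-size or error-rate figure is involved. The check pairs the mock-up's cells and compares them with the definition.

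**1. Is the mapping an artefact of a broken table?** Listing 24 has 13 source cells and 13 label cells, and they pair without a shift. Column 4 (last contact) comes from the end-of-study form, column 6 (date of first discontinuation) from the four adverse-event dates, column 8 (progression) from the tumor staging date, and column 10 (death) from the end-of-study form. The three yes/no flags and the PFS, OS and TFTS columns are blank. The mapping is as it appears.

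**2. Which TFTS reasons can be dated from Listing 24?**

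| Reason under SAP 4.12 | Date in Listing 24 |
|---|---|
| Progression | Own column |
| Death | Own column |
| Loss to follow-up | Last-contact column |
| Toxicity | Four adverse-event dates, drug by drug |
| Consent withdrawal | No discontinuation date; last contact can approximate it if the patient leaves the study |
| Patient preference | No discontinuation date; last contact helps only if the patient leaves the study |
| Other reasons, such as an investigator or sponsor decision | As for patient preference |

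**3. Can a patient stop treatment and stay in the study?** Yes. Protocol 5.4.1 and SAP 4.20 keep patients in follow-up after permanent discontinuation unless they withdraw. Protocol 7.6 then records new therapy, survival and adverse events, without scheduled imaging. For such a patient the usual dates left in Listing 24 are last contact and death, and neither is the end of treatment.

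**4. What happens with a single-drug date?** If one drug is stopped for toxicity and the others go on, the first of the four dates precedes the end of treatment. Protocol 5.1 foresees that situation, and Protocol 6.2 foresees it for cetuximab. The documents do not define the inter_date fields. If they also hold temporary interruptions, the conflict with Protocol 5.4.1 is wider; this cannot be settled without the case report form.

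**5. Do better sources exist?** Yes. The end-of-treatment reason is mapped in Listing 25.1, administration dates in Listings 22.2 to 22.6, and withdrawal and last-contact dates in Listing 27. The end-of-treatment visit date would not do, because Protocol 7.5 sets that visit 30±2 days after the last medication. With the SAP's month of 30.4 days, using it would lengthen TFTS by (30 − 2)/30.4 = 0.92 to (30 + 2)/30.4 = 1.05 months.

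**The case against.** The strongest reply is that a pointer is not a derivation. SAP 4.12 states the endpoint correctly, and a careful programmer would follow it over a grey field name. That is fair, and it is why the point is minor. It does not remove the conflict: the listing names no other source for this column, and SAP 4.12 gives no rule for combining the listed dates into TFTS.

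The second reply is that the meaning of inter_date is unknown and that Listing 28.1 maps a per-drug action-taken field that might separate interruptions from stops. This stands. The single-drug error is therefore something that could happen, not something shown.

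Several stronger readings are tempting, and the documents do not support them:

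- A reader might infer that every stop without an adverse event goes undated. Progression, death and last contact have their own columns.
- A reader might take the blank source of the any-reason flag as a further omission. The progression and death flags and the three derived times are blank too.
- A reader might infer that dating a permanent cetuximab stop is plainly wrong. SAP 4.12 does not say whether discontinuation means one drug or the whole strategy, so that case is unsettled.
- A reader might add a missing censoring rule at study closure and the handling of 36-month completion. Protocol 5.4.1 lists study closure, and SAP 4.20 lists three years of treatment, among the reasons for permanent discontinuation. On the text both can be read as events, and another treatment of them is a preference.
- A reader might infer a bias against Arm A, since only that arm receives cetuximab. Neither its size nor its direction can be derived.

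**Conclusion.** Wrong as written, but minor. The stated source for the discontinuation date does not match the definition of TFTS. The certain part is a stop without an adverse event, progression or death in a patient who stays in follow-up: the column as mapped gives that patient no date. The conditional part is a single-drug date taken as the end of the strategy; it depends on how the programmer uses the four fields and on what they record.

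The reach is Listing 24 and Figure 4. SAP 4.2 reports seven patients enlisted, so at most seven TFTS values are involved; the number randomized and the split by arm are not given. No test or interval estimate rests on TFTS. Dosing dates and end-of-treatment reasons are printed in other listings, so a reader could detect a misdated value. No document shows that such a patient exists. Counting the stop reasons in Protocol 5.4.1 would not measure how many patients are affected.

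**What to change.** In Listing 24, replace the adverse-event-only source with the permanent end of all study treatment:

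- Identify it from the end-of-treatment reason (Listing 25.1).
- Date it from the last administration of any study drug (Listings 22.2 to 22.6). For consent withdrawal or loss to follow-up, use the withdrawal or last-contact date (Listing 27).
- Do not use the end-of-treatment visit date.

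In SAP 4.12, state that TFTS runs from randomization to the earliest of that date, RECIST progression or death, and that temporary interruptions and RAS-guided cetuximab switches are not events. Reconcile Protocol 5.1, 5.4.1 and 6.2 with SAP 4.12 on how a permanent single-drug stop is counted, including cetuximab in Arm A. The sponsor should settle that and write it down.

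The cost is a few lines of SAP text, one mock-up and the matching program. The fields named are already mapped in other listings, so no new data are needed.

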**Listing 25.2: EOT - RAS mutation status**

patient.patient_no	registration.registration_arm_randomized	eut.eot_ras_mutation_status_done	eut.eot_ras_mutation_status	eut.eot_kras	eut.eot_kras_mutation_list	eut.eot_nrás	eut.eot_nrás_mutation_list
Patient No.	Arm	Results of RAS mutation status available [yes/no]	Mutation status [wt/mutant]	KRAS detected [yes/no]	Exon(s) and Codon(s) of KRAS mutation(s)	NRAS detected [yes/no]	Exon(s) and Codon(s) of NRAS mutation(s)

Follow-up visits:**Listing 26.1: Follow-up visit - first part**

patient.patient_no	registration.registration_on_arm_randomized	followup.followup_no	followup.followup_date	followup.followup_contact	followup.followup_tumor_th	tumor.tumor_therapy	tumor.tumor_start	tumor.tumor_end(nd)
Patient No.	Arm	Follow-up No.	Follow-up visit date	Contact with patient	Changes in new therapy since last visit [yes/no]	New therapy	Start date of new therapy	End date of new therapy

**Listing 26.2: Follow-up visit - second part**

patient.patient_no	registration.registration_on_arm_randomized	followup.followup_no	followup.followup_surgery_taken		followup.followup_surgery_date	followup.followup_surgery_type
Patient No.	Arm	Follow-up No.	Resection of metastases since last visit [yes/no]		Date of resection	Which metastasis were resected

End of study:**Listing 27: End of study**

patient.patient_no	registration.registration_on_arm_randomized	endofstudy.endofstudy_last_contact_date	endofstudy.endofstudy_reason(_spec)	endofstudy.endofstudy_death_date	endofstudy.endofstudy_death_reason(_spec)				icd10_en2010_code.description	endofstudy.endofstudy_withdrawal_date	endofstudy.endofstudy_withdrawal_reason
Patient No.	Arm	Date of last contact	Reason for end of study	Date of death if applicable	Reason of death if applicable	Death related AE if applicable			Death related disease if applicable	Date of withdrawal if applicable	Reason of withdrawal if applicable
						ae.ae_nci	nci_v5_ae.eae	ae.ae_nci_text			
						Grade	Term	Other			

Adverse events:**Listing 28.1: AEs/toxicity - terminology, timeline, and causality**

[figure not shown]
patient.patient_no	registration.registration_arm_randomized				ae.ae_start(_na)	ae.ae_end(_na)	ae.ae_outcome	ae.ae_treatment_started		ae.ae_irino_causal, ae.ae_fa_causal, ae.ae_ffu_causal, ae.ae_ce_causal	ae.ae_irin_o_action, ae.ae_fa_action, ae.ae_ffu_action, ae.ae_ce_action	ae.ae_medication_treated
Patient No.	Arm	Terminology according to CTCAE version 5			Start date	End date	Outcome	Study treatment started [yes/no]	Study treatment component	Causal relationship suspected [yes/no]	Action taken	Event treated with medication [yes/no]
		ae.ae_nci	nci_v5_ae.ae	ae.ae_nci_text								
		Grade	Term	Other								

[figure not shown]
**Listing 28.2: AEs/toxicity - SAEs and special AEs**

[figure not shown]
patient.patient_no	registration.registration_arm_randomized		ae.ae_start(_na)	ae.ae_sae	ae.ae_criteria_fatal, ae.ae_criteria_life_threatening, ae.ae_criteria_hospital, ae.ae_criteria_disability, ae.ae_criteria_congenital, ae.ae_criteria_important_event(_spec)	ae.ae_special	ae.ae_criteria_pregnancy, ae.ae_criteria_error
Patient No.	Arm	Terminology according to CTCAE version 5		Start date	Serious AE [yes/no]	Reason for classification as serious	Special event [yes/no]
		ae.ae_n_ci Grade	nci_v5_ae.ae_n_ci_t_ext Term	Oth er			Reason for classification as special

[figure not shown]
### 5.3 Figures

**Figure 1: Swimmer plot**

Figure	Figure 1	Example (no study data)
Title 1	Treatment and response timeline	
Title 2	for each randomized patient	
Type of graph	Swimmer plot	
y-axis	Patient numbers.	
y-axis (label)	Study participants	
x-axis	0 to maximum rounded up number to nearest month	
x-axis (label)	Treatment duration in months	
Legend	Study treatment: (m)FOLFIRI, (m)FOLFIRI + cetuximab, Treatment response: CR, PR, SD, PD, and death	
Footnote	The gray arrow indicates continuing response.	
Additional information	-	 
The gray arrow indicates continuing response.

**Figure 2: Progression-free survival (PFS) [months]**

**Figure 3: Overall survival (OS) [months]**

**Figure 4: Time to failure of treatment strategy (TFTS) [months]**

## 6 Statistical software

All descriptive statistical analyses will be performed by using the statistical software SAS version 9.4.

## 7 Medical dictionaries

As medical dictionary for analysis we use the latest available version of MedDRA and ICD10.

## 8 Coding conventions

There are no special coding conventions.

## 9 Output format

If a statistical report will be written, the respective tables and figures will be presented in the text. The text will be written in Arial 11 pt with 1.0 line spacing with exceptions to title and signature pages. The TLF will be written in Arial 10 pt and dates contained in TLF will be given in DDMMYY format.

## 10 List of the tables, listings, and figures planned for the Final Statistical Report

### Tables:

- Table 1: General data
- Table 2: Patients' first conversion to RAS wild-type
- Table 3: Patient responses
- (Optionally) Table 4.1: AEs - overview
- (Optionally) Table 4.2: AEs - System Organ Class (SOC) and Preferred Term (PT) by NCI CTCAE grade
- (Optionally) Table 4.3: AEs - number of patients with respect to System Organ Class (SOC) and Preferred Term (PT) by maximal NCI CTCAE grade

### Listings:

- Listing 1.1: Inclusion criteria
- Listing 1.2: Inclusion criteria 01-09
- Listing 1.3: Inclusion criteria 10-19
- Listing 2.1: Exclusion criteria
- Listing 2.2: Exclusion criteria 01-08
- Listing 2.3: Exclusion criteria 09-15
- Listing 2.4: Exclusion criteria 16-22
- Listing 3: Eligibility, enrollment, and randomization
- Listing 4: Patient demographics
- Listing 5.1: Initial diagnosis of mCRC - TNM staging
- Listing 5.2: Initial diagnosis of mCRC - resection
- Listing 5.3: Initial diagnosis of mCRC - RAS mutation analysis
- Listing 6: Medical history
- Listing 7.1: Relevant medication - premedication
- Listing 7.2: Relevant medication - concomitant medication
- Listing 8: Baseline echocardiography
- Listing 9: Baseline TNM staging
- Listing 10: Baseline coagulation parameters
- Listing 11: Baseline DPD deficiency
- Listing 12: Baseline hepatitis serology
- Listing 13: ECG assessments
- Listing 14: ECOG performance statuses

- Listing 15: Vital signs
- Listing 16: Hematological lab assessments
- Listing 17.1: Blood chemistry lab assessments - first part
- Listing 17.2: Blood chemistry lab assessments - second part
- Listing 18: Tumor markers lab assessments
- Listing 19: RAS mutation analyses on tumor tissue
- Listing 20.1: Samplings for liquid biopsy
- Listing 20.2: Samplings for liquid biopsy - RAS mutation status
- Listing 20.3: Samplings for liquid biopsy - first conversion to RASwt
- Listing 21:  $\beta$ -HCG pregnancy tests
- Listing 22.1: Treatment cycles - general
- Listing 22.2: Treatment cycles - irinotecan (iv infusion, 180mg/m^2 over 90 min)
- Listing 22.3: Treatment cycles - folinic acid (iv infusion, 400mg/m^2 over 120 min)
- Listing 22.4: Treatment cycles - 5-FU (bolus, 400mg/m^2)
- Listing 22.5: Treatment cycles - 5-FU (iv infusion, 2400mg/m^2 over 46h)
- Listing 22.6: Treatment cycles - cetuximab (iv infusion, initially 400 mg/m^2 over 120 min, subsequently 250 mg/m^2 over 60 min)
- Listing 23.1: RECIST assessments
- Listing 23.2: RECIST assessments - lesions
- Listing 24: PFS, OS, and TFTS
- Listing 25.1: EOT - resection and new therapy
- Listing 25.2: EOT - RAS mutation status
- Listing 26.1: Follow-up visit - first part
- Listing 26.2: Follow-up visit - second part
- Listing 27: End of study
- Listing 28.1: AEs/toxicity - terminology, timeline, and causality
- Listing 28.2: AEs/toxicity - SAEs and special AEs

Figures:

- Figure 1: Swimmer plot
- Figure 2: Progression-free survival (PFS) [months]
- Figure 3: Overall survival (OS) [months]
- Figure 4: Time to failure of treatment strategy (TFTS) [months]

